### 6.3.4 Recording of adverse events

#### Time period for collection of adverse events

For patients who do not enroll in an extension study, all AEs will be collected from the time of signature of informed consent to the follow-up visit (Visit 5), whether or not related to the IP and must be recorded on the eCRF. Unsolicited reports of SAEs will also be collected for 30 days after the last dose of study drug.

For patients who enroll in an extension study, AEs and SAEs will be collected from the time of signature of informed consent to the last treatment visit (Visit 4), whether or not related to

the IP and must be recorded on the eCRF. Additional AE and SAE reporting will occur in the extension study.

#### Follow-up of unresolved adverse events

Any AEs that are unresolved at the patient's last AE assessment in the study are followed up by the investigator for as long as medically indicated, but without further recording in the eCRF. AstraZeneca or its representative retains the right to request additional information for any patient with ongoing AE(s)/SAE(s) at the end of the study, if judged necessary.

#### Variables

The following variables will be collected for each AE:

- AE (verbatim)
- The date when the AE started and stopped
- Maximum intensity or intensity or changes in intensity
- Whether the AE is serious or not
- Investigator causality rating against the study drug (yes or no)
- Action taken with regard to IP
- AE caused patient's discontinuation from study (yes or no)
- Outcome

In addition, the following variables will be collected for SAEs:

- Date AE met criteria for SAE
- Date investigator became aware of SAE
- Seriousness criteria
- Date of hospitalization
- Date of discharge
- Probable cause of death
- Date of death
- Autopsy performed

- Causality assessment in relation to study procedure(s)
- Causality assessment in relation to other medication
- Description of AE (including treatment administered and dechallenge/rechallenge information, if applicable)

Intensity is defined as follows:

- Mild (awareness of sign or symptom, but easily tolerated)
- Moderate (discomfort sufficient to cause interference with normal activities)
- Severe (incapacitating, with inability to perform normal activities)

#### Other reporting guidance

It is important to distinguish between serious and severe AEs. Severity is a measure of intensity whereas seriousness is defined by the criteria in Section 6.3.3. An AE of severe intensity need not necessarily be considered serious. For example, nausea that persists for several hours may be considered severe nausea, but not an SAE. On the other hand, a stroke that results in only a limited degree of disability may be considered a mild stroke, but would be an SAE.

If a diagnosis of the patient's condition has been made, then the diagnosis should be recorded as the SAE or the AE. In instances of well-recognized symptoms, they can be recorded as the commonly used diagnosis (eg, fever, runny nose, and cough can be recorded as "flu"). However, if a diagnosis of the patient's condition has not been made, or if the individual symptoms are not well recognized, then the individual symptoms should be recorded separately.

Should an overdose occur, it must be reported in accordance with the procedures described in Section 13.2. All overdoses, with or without associated symptoms, should be reported as AEs.

Suicide and attempted suicide, irrespective of the method, but occurring in connection with the use of study drug, should be reported as AEs (serious or nonserious). The event should be identified as suicide or attempted suicide, and the method of the suicide or attempt should be provided. If an attempted suicide meets the criteria for an SAE, the event must be reported according to the guidelines in Section 6.3.5. Suicidal thoughts and preparation for suicide should also be regarded as AEs. All events of suicidality will be monitored via the C-SSRS.

Pregnancy in itself is not regarded as an AE unless there is a suspicion that the IP has interfered with the effectiveness of a contraceptive medication. (To be eligible for this study, WOCBP and at risk of pregnancy must be using a reliable method of contraception; see Inclusion Criterion #6, Section 4.1). Should a pregnancy occur, it must be reported in accordance with the procedures described in Section 13.3.

In the clinical study report (CSR), the terms used by the investigator to record AEs will be mapped to preferred terms using a standard AE dictionary, Medical Dictionary for Regulatory Activities (MedDRA).

### **Causality collection**

The investigator will assess causal relationship between IP and each AE (ie, their relationship to study drug), and answer "yes" or "no" to the question, "*Do you consider that there is a reasonable possibility that the event may have been caused by the investigational product*?"

For SAEs, causal relationship will also be assessed for other medication and study procedures. Note that for SAEs that could be associated with any study procedure, the causal relationship is implied as "yes."

A guide to the interpretation of the causality question is found in Appendix B to the CSP.

#### Adverse events based on signs and symptoms

All AEs spontaneously reported by the patient or reported in response to the open question from the study personnel: "*Have you had any health problems since the previous visit/you were last asked?*," or revealed by observation will be collected and recorded in the eCRF. When collecting AEs, the recording of diagnoses is preferred (when possible) to recording a list of signs and symptoms. However, if a diagnosis is known and there are other signs or symptoms that are not generally part of the diagnosis, the diagnosis and each sign or symptom will be recorded separately.

#### Adverse events based on examinations and tests

The results from protocol-mandated laboratory tests and vital signs will be summarized in the CSR. Deterioration as compared to baseline in protocol-mandated laboratory values, and vital signs should therefore only be reported as AEs if they fulfill any of the AE criteria or are the reason for discontinuation of treatment with the IP, or at the discretion of the investigator.

If deterioration in a laboratory value/vital sign is associated with clinical signs and symptoms, the sign or symptom will be reported as an AE and the associated laboratory result/vital sign will be considered as additional information. Wherever possible, the reporting investigator uses the clinical, rather than the laboratory term (eg, anaemia versus low Hb value). In the absence of clinical signs or symptoms, clinically relevant deteriorations in non-mandated parameters should be reported as AE(s).

Deterioration of a laboratory value, which is unequivocally due to disease progression, should not be reported as an AE/SAE.

Any new or aggravated clinically relevant abnormal medical finding at a physical examination as compared with the baseline assessment will be reported as an AE.

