#### 6.3.2 Definition of adverse events

An AE is the development of an undesirable medical condition or the deterioration/exacerbation of a pre-existing medical condition following or during exposure to a pharmaceutical product, whether or not considered causally related to the product. An undesirable medical condition can be symptoms (eg, nausea, chest pain), signs (eg, tachycardia, enlarged liver), or the abnormal results of an investigation (eg, laboratory findings, ECG). In clinical studies, an AE can include an undesirable medical condition occurring at any time, including run-in or washout periods, even if no study treatment has been administered.

The term AE is used to include both serious and non-serious AEs.

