#### 6.3.3 Definitions of serious adverse event

An SAE is an AE occurring during any study phase (ie, run-in, treatment, washout, follow-up), that fulfills 1 or more of the following criteria:

- Results in death
- Is immediately life-threatening
- Requires in-patient hospitalization or prolongation of existing hospitalization
- Results in persistent or significant disability/incapacity or substantial disruption of the ability to conduct normal life functions
- Is a congenital abnormality or birth defect
- Is an important medical event that may jeopardize the patient or may require medical intervention to prevent 1 of the outcomes listed above

For further guidance on the definition of an SAE, see Appendix B to the CSP.

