#### Underlying disease progression

Disease progression can be considered as a worsening of a patient's condition attributable to the disease for which the IP is being studied, which in this study refers to the condition of OIC. Adverse events which are due to disease (ie, OIC) progression, in the opinion of the investigator, should not be reported as an AE, unless they meet SAE criteria (eg, hospitalization, etc (see Section 6.3.3).

Of note, patients in this study must have an opioid-requiring pain condition in order to participate. Any day-to-day type fluctuations in pain control common in this population should not be reported as AEs, unless they meet SAE criteria (eg, hospitalization, etc., see Section 6.3.3).

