#### 6.3.5 Reporting of serious adverse events

All SAEs have to be reported, whether or not considered causally related to the IP, or to the study procedure(s). All SAEs will be recorded in the eCRF.

If any SAE occurs in the course of the study, then investigators or other study site personnel must inform appropriate AstraZeneca representatives within 1 day, ie, immediately, but **no** later than the end of the next business day of when he or she becomes aware of it.

The designated AstraZeneca representative works with the investigator to ensure that all the necessary information is provided to the AstraZeneca Patient Safety data entry site within **1 calendar day** of initial receipt for fatal and life-threatening events **and within 5 calendar days** of initial receipt for all other SAEs.

For fatal or life-threatening AEs where important or relevant information is missing, active follow-up is undertaken immediately. Investigators or other study site personnel must inform AstraZeneca representatives of any follow-up information on a previously reported SAE within 1 calendar day, ie, immediately, but **no later than the end of the next business day** of when he or she becomes aware of it.

If the eDC system is not available, then the investigator or the other study site personnel reports an SAE to the appropriate AstraZeneca representative by telephone.

The AstraZeneca representative will advise the investigator/study site personnel how to proceed.

Refer to the study-specific Safety Handling Plan for details on SAE reporting using the eDC system.

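### Section 6.3.4 bars reporting a laboratory deterioration due to disease progression even as an SAE, contradicting its next subsection and Section 6.3.5; the gap is narrow

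*Protocol*

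**What the plan says.** Five places in the protocol bear on this point.

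- **Section 6.3.4, Adverse events based on examinations and tests.** The last of the laboratory rules reads: "Deterioration of a laboratory value, which is unequivocally due to disease progression, should not be reported as an AE/SAE". The wording covers both AE and SAE and has no exception.
- **Section 6.3.4, Underlying disease progression.** This is the next subsection. It defines progression as worsening of the disease for which the drug is studied, "which in this study refers to the condition of OIC". Events that the investigator attributes to it "should not be reported as an AE, unless they meet SAE criteria (eg, hospitalization, etc (see Section 6.3.3)".
- **Section 6.3.5.** The general rule on serious events is "All SAEs have to be reported, whether or not considered causally related to the IP, or to the study procedure(s)".
- **Section 6.3.2.** An AE can consist of a symptom, a sign "or the abnormal results of an investigation (eg, laboratory findings, ECG)".
- **Section 6.3.3.** "An SAE is an AE occurring during any study phase (ie, run-in, treatment, washout, follow-up), that fulfills 1 or more of the following criteria". The list that follows has no exemption for disease progression.

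SAEs are a safety variable in Section 6.3.1 and are tabulated by treatment group under Section 12.2.1.

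**The concern.** A site needs one answer to the question of whether a serious event goes on the SAE form. For one class of event, the protocol gives two. A site that follows the laboratory sentence literally files nothing. A site that follows the next subsection or Section 6.3.5 files an SAE.

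The primary objective is long-term safety and tolerability (Section 2.1), and Section 12.2 plans descriptive statistics only. The tabulated counts are therefore themselves the result, and an instruction that tells sites to leave a serious event out of them should not stand. A later analysis plan cannot repair this, because an SAE that was never reported is not in the SAE data to be counted.

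**Working it through.** No arithmetic applies. The protocol gives no rate for these events and no figure to reproduce, so the check is a comparison of the rules.

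**Step 1: the test case.** Take a laboratory deterioration that (a) the investigator considers unequivocally due to worsening OIC and (b) meets a seriousness criterion in Section 6.3.3, such as hospitalization or an important medical event.

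**Step 2: apply each rule.**

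| Protocol text | Instruction for the test case |
|---|---|
| 6.3.4, examinations and tests | Do not report, either as AE or as SAE |
| 6.3.4, underlying disease progression | Report, because SAE criteria are met |
| 6.3.5 | Report; all SAEs, whatever the cause |

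The first row cannot be followed together with the other two.

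**Step 3: can the rules be read together?** One route is to say that progression is not an AE and so, under Section 6.3.3, cannot be an SAE. The protocol closes that route. Its subsection on disease progression expressly keeps progression events reportable once SAE criteria are met. Section 6.3.2 counts both abnormal laboratory findings and the deterioration of an existing condition as possible AEs. Appendix B points the same way: it deals with deterioration of the disease under study due to lack of effect through the causality answer, not by leaving the event out. The laboratory sentence is the outlier.

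**Step 4: how many cases does the conflict reach?** Two rules shrink it.

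- Disease progression means OIC only, and the attribution must be unequivocal.
- Section 6.3.4 says that when a laboratory deterioration comes with clinical signs or symptoms, the sign or symptom is the reported event and the laboratory result is supporting information. If that clinical event is serious, the disease-progression subsection makes it reportable.

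What is left is mainly a laboratory deterioration without reportable signs or symptoms that still meets a seriousness criterion and is attributed to OIC.

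**Step 5: which text conflicts?** The paragraph directly after the laboratory sentence concerns physical examination findings and is consistent with it. The conflict is with the next subsection and with Section 6.3.5.

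**The case against.** The strongest reply is that almost nothing falls into the gap. OIC is defined by symptoms, and the protocol presents none of the tests in Table 4 as a measure of it. A patient admitted with severe constipation and an abnormal laboratory value has symptoms, so that admission reaches the SAE listing under a clinical term. A site that reads all the rules would probably report, since Section 6.3.5 is the general SAE rule and the disease-progression subsection is the specific one. Other records also hold part of the picture. Central laboratory values are summarized by treatment group with shifts and outliers (Sections 12.2 and 12.2.1). Inpatient contacts for OIC are collected on the resource utilization form (Section 6.9.2) and tabulated (Section 12.2.3).

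Most of this stands, and it fixes the size of the point. It does not remove the contradiction. After enrollment, routine chemistry and hematology are scheduled only at Visits 4 and 5 (Section 6.3.10), and patients who enter the 52-week extension skip Visit 5. Section 6.9.2 itself says that the resource utilization form is not to be used for AE reporting. Neither source replaces an SAE report. That a careful site would probably choose correctly is no reason to leave the wrong instruction in place.

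A reader might also infer that the sentence suppresses expedited reports. The documents do not support that. Section 5.4.2 links potential expedited reporting to unexpected SAEs suspected of being caused by the drug, and an event judged unequivocally due to OIC would not ordinarily be suspected of that.

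**Conclusion.** The contradiction is real and the laboratory sentence is wrong as written. It tells sites to withhold a class of serious event that the next subsection and Section 6.3.5 tell them to report. This rests on the wording alone and needs no assumption about event rates.

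Its reach is small: mainly isolated laboratory deteriorations that meet an SAE criterion and are attributed to OIC. A reader might go further and infer a material bias in SAE incidence, or a difference between arms because the exemption depends on the condition under treatment. The documents do not support either inference. They give no rate for such events, and they show neither a direction nor a size for any imbalance, so no change in an arm's SAE percentage can be stated. This is a minor internal inconsistency in safety reporting, worth correcting because safety is the primary objective and the correction is simple.

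**What to change.** Reconcile the laboratory sentence in Section 6.3.4 with the disease-progression subsection and Section 6.3.5 by giving it the same exception. It should say that a laboratory deterioration unequivocally due to disease progression is not reported as an AE unless it meets SAE criteria (Section 6.3.3), in which case it is reported under Section 6.3.5. The combined term AE/SAE drops out of the sentence.

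The cost is one clause in the protocol and a line in site training. A few more SAE reports are possible. Design, endpoints, visit schedule and patient care do not change.

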#### Underlying disease progression

Disease progression can be considered as a worsening of a patient's condition attributable to the disease for which the IP is being studied, which in this study refers to the condition of OIC. Adverse events which are due to disease (ie, OIC) progression, in the opinion of the investigator, should not be reported as an AE, unless they meet SAE criteria (eg, hospitalization, etc (see Section 6.3.3).

Of note, patients in this study must have an opioid-requiring pain condition in order to participate. Any day-to-day type fluctuations in pain control common in this population should not be reported as AEs, unless they meet SAE criteria (eg, hospitalization, etc., see Section 6.3.3).

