# **1. INTRODUCTION**

### 1.1 Background

Physiologic effects of opioids on the gastrointestinal (GI) system include decreased gastric motility and gastric emptying, diminished intestinal secretions, and decreased peristalsis in the colon which sometimes may lead to constipation and other abdominal symptoms. Complications of opioid therapy may include fecal impaction, pseudo-obstruction, and hindrance of drug absorption. In the United States (US), patients with a variety of underlying conditions receive in aggregate, a total of approximately 1.2 billion patient days of opioid therapy for pain that is treated for at least 15 days. Estimates of the incidence of constipation within the population of patients taking opioids vary widely (15% to 90%) with differences attributed to varying opioid agents, varying doses, differing underlying diagnoses, and differing criteria used to define constipation.

A well-tolerated and efficacious orally-administered treatment option for constipation due to treatment with opioids remains a major unmet medical need for patients being treated for pain. Current treatment for opioid-induced constipation (OIC) - which includes laxatives, stool softeners, and, if necessary, reflex evacuation via enema - is distinctly sub-optimal, with up to 46% of patients not achieving the desired treatment outcome (Pappagallo 2001). Furthermore, a number of the conventional therapeutic interventions are, quite often, inconvenient at best (eg, enemas, lactulose) and, in some cases impractical. For example, debilitated patients may be unable to self-administer an enema, and a constipated patient with severely inflamed hemorrhoids or neutropenia would not be an ideal candidate for an enema. Fiber supplementation with psyllium requires patients to drink ample quantities of water, which is not always possible. Although generally well-tolerated, side-effects of various treatments for constipation include bloating (lactulose, fiber supplements, and polyethylene glycol [PEG]), cramps, abdominal pain, nausea, diarrhea, dehydration, and electrolyte imbalances.

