AstraZeneca is developing NKTR-118, a peripherally acting  $\mu$ -opioid antagonist, for the treatment of OIC. NKTR-118 is a PEGylated derivative of naloxone; introduction of the PEG moiety reduces the ability of naloxone to enter the central nervous system (CNS). In the periphery, NKTR-118 targets  $\mu$ -opioid receptors in the enteric nervous system, which mediate OIC. NKTR-118 represents, potentially, the first oral drug in a novel class of therapeutic agents for the specific treatment of OIC. It is hoped that this investigational agent will prove to be practical and convenient, highly effective, and well-tolerated in patients with OIC.

Previous studies have shown that NKTR-118 alleviates symptoms of OIC while preserving the central analgesic effect of opioid therapy. For example, in a Phase II study, in which doses of NKTR-118 5, 25, and 50 mg/day were evaluated against placebo over the course of 4 weeks, NKTR-118 reversed symptoms of OIC as measured by increase in spontaneous bowel movements (SBMs) in patients receiving a wide range of opioid doses for pain. For the 25 mg/day dose group and 50 mg/day dose group, the change from baseline in SBMs per week to the end of Week 1 was 3.6 and 4.4. In the placebo group, the corresponding change

from baseline was 1.9. NKTR-118 was well-tolerated in the Phase II study at 5 and 25 mg/day with the most commonly reported side effects being GI in nature (abdominal pain, diarrhea, and nausea) and most frequent in the 50 mg cohort. No reversal of analgesia or central opioid withdrawal symptoms were seen at any doses tested in the Phase II study.

Based on the above, it is appropriate to proceed with studying the long term effect of NKTR-118 in the target population, that is, patients receiving opioid therapy for pain who are experiencing OIC. This study will evaluate the safety and tolerability of NKTR-118 12.5 and 25 mg when treatment is extended over a treatment period of 6 months. The patients enrolling in this study will be participants in the AstraZenenca pivotal Phase III study who are willing to continue the treatment they are receiving in the pivotal study for another 12 weeks. The duration of the Phase III pivotal study is 12 weeks; thus, combined, the entire treatment period for those participating in the current study will be 24 weeks (6 months). For a detailed description of pre-clinical data, and the results of prior human studies in healthy subjects, please refer to the Investigator's Brochure (IB).

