# 2. STUDY OBJECTIVES

# 2.1 **Primary objective**

The primary objective of this study is to compare NKTR-118 12.5 and 25 mg with placebo regarding long-term safety and tolerability in the treatment of OIC using descriptive statistics.

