# 6.4.1.1 PAC-SYM

The PAC-SYM questionnaire (Frank et al 1999) is a 12-item questionnaire that evaluates the severity of symptoms of constipation in 3 domains (stool, rectal, and abdominal symptoms) on a 5-point Likert scale ranging from 0 (absent) to 4 (very severe) in the 2 weeks (14 days) prior to assessment. The items of the instrument were developed through literature review and patient interviews. The PAC-SYM has been extensively validated for constipation and is available in several languages that facilitate its use in multinational studies. The translations into local languages have been performed according to a linguistic validation process. The questions will take approximately 5 minutes to answer. The patients need to be able to read and to be fluent in the local language. The PAC-SYM will be administered to patients at Visit 1 (enrollment - data obtained at the Visit 8 of previous study D3820C00004), Visit 2 (Week 4), Visit 4 (Week 12/early termination), and Visit 5 (Week 14).

The PAC-SYM questionnaire will be completed by patients on the SitePad device provided at the study center. Study staff will log patients in. Patients are to fill out the questionnaire in a quiet area, without any help from family, friends, or study staff. With the exception of Visit 1, where some interaction with staff will be necessary in order to ensure that enrollment criteria

have been met, patients are to fill out the PAC-SYM questionnaire prior to any interventions or discussions regarding their OIC with the study staff or the investigator.

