# 11. EVALUATION AND CALCULATION OF VARIABLES

## **11.1** Calculation or derivation of efficacy variable(s)

## 11.1.1 PAC-SYM

For the PAC-SYM, each item is scored as 0=absence of symptom, 1=mild, 2=moderate, 3=severe, and 4=very severe. The 12 items of the PAC-SYM are assigned to 3 domains:

- Abdominal symptoms (items 1 to 4)
- Rectal symptoms (items 5 to 7)
- Stool symptoms (items 8 to 12).

Each domain score will be calculated as the mean of the non-missing items for that domain. The total score will be calculated as the mean of all non-missing items. If more than 50% of values for a domain or the total score are missing for a visit, the values for that score will be set to missing.

Change from baseline in the PAC-SYM domain and total scores will be calculated for Weeks 4, 12, and 14 as the post-baseline value minus the baseline value. Negative changes from baseline indicate improvement.

The primary baseline PAC-SYM values will be defined as the latest non-missing value collected prior to the first dose of study drug in the previous pivotal study (D3820C00004) (screening, Visit 1 or Week 0, Visit 3), and supportive baseline PAC-SYM values will be defined as the data collected at Visit 8 from the previous study D3820C00004 (also defined as Visit 1 of this study).

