## **11.2** Calculation or derivation of safety variable(s)

## 11.2.1 Adverse events

A treatment-emergent adverse event (TEAE) is defined as any AE that started on or after the first dose of study drug up to the last dose of study drug. An AE already present at the time of the first dose of study drug that worsens in intensity following exposure to study drug or an AE with an unknown/not reported onset date will also be considered as treatment-emergent. Adverse events occurring after the last dose of study drug will also be summarized, which among other purposes, may assess any potential withdrawal-type effects.

Time to onset of an AE (in days) will be calculated as:

AE start date - Date of the first dose of study drug + 1.

Duration of an AE (in days) will be calculated as:

AE resolution date - AE start date + 1.

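### Cheap improvement: Section 6.3.4 lets the investigator's opinion keep non-serious abdominal pain off the AE form as OIC progression; limit that exemption to constipation itself

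*Protocol*

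**What the plan says.** Under Underlying disease progression, Section 6.3.4 describes progression as any worsening of the patient's condition attributable to OIC. It then says that events "due to disease (ie, OIC) progression, in the opinion of the investigator, should not be reported as an AE, unless they meet SAE criteria". It gives no list of symptoms, and meeting SAE criteria is the only exception.

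On the disease side, Section 1.1 describes the bowel effects of opioids as including "decreased peristalsis in the colon which sometimes may lead to constipation and other abdominal symptoms". Section 6.4.1.1 says that the PAC-SYM "evaluates the severity of symptoms of constipation in 3 domains (stool, rectal, and abdominal symptoms", and Section 11.1.1 sets up a domain "Abdominal symptoms (items 1 to 4".

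On the drug side, Sections 1.1 and 1.4 report the Phase II experience as the "most commonly reported side effects being GI in nature (abdominal pain, diarrhea, and nausea". Section 5.8 repeats that abdominal pain was reported as an AE in an earlier trial of the drug.

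The primary objective (Section 2.1) is to compare both doses with placebo for "long-term safety and tolerability in the treatment of OIC using descriptive statistics". Section 6.3.1 puts AE incidence first among the safety variables and names AEs leading to discontinuation. Section 12.2.1 tabulates both by treatment group, and also tabulates AEs by causality.

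**The concern.** Apart from this exemption, the protocol records first and attributes afterwards. AEs are collected irrespective of relatedness, the investigator answers a causality question for each one, and a table by causality is produced. The progression rule reverses that order for one class of event, because the investigator's view of the cause decides whether a record exists at all.

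That does little harm where the event can only be constipation. Abdominal pain and cramping can reasonably be read either way. Under one reading the event enters the AE tables with onset, intensity, causality and action taken. Under the other it leaves no AE record, and no later analysis can bring it back. The study exists to describe tolerability against placebo, and this is one of the symptoms on which tolerability of this drug is judged.

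**Working it through.** The protocol plans no statistical testing and has no sample size calculation, so there is no stated figure to reproduce. The check is a reading of the text, with two small pieces of arithmetic.

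**1. Can non-serious abdominal pain fall under the exemption?** It needs only a judgement that the event is due to worsening OIC. Sections 1.1, 6.4.1.1 and 11.1.1 make abdominal symptoms part of the condition, so the judgement is open to the investigator. Nothing in Section 6.3.4 excludes pain or cramping from it.

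**2. Can the same pain be a drug effect?** Yes. Sections 1.1, 1.4 and 5.8 say so.

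**3. Does a later step recover it?** The causality question, the Appendix B guide and the by-causality table in Section 12.2.1 all operate on recorded AEs. An exempted event reaches none of them.

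**4. What if the event ends treatment?** The exemption excepts SAEs only. A non-serious abdominal pain that led a patient to stop study drug could, if called OIC progression, be missing from the count of AEs leading to discontinuation.

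**5. What happens to the comparison?** Let p be the true proportion of patients with the event in an arm, and s the share of those patients whose events are all exempted. The tabulated proportion is p × (1 − s). The tabulated difference is p_active × (1 − s_active) − p_placebo × (1 − s_placebo).
- Each arm's proportion can only fall or stay the same.
- If s is equal in all arms, the difference shrinks by the factor (1 − s).
- If s differs between arms, the difference can move either way.

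The protocol gives neither p for abdominal pain by arm nor any s. The nearest rates, in Section 1.4, are for any GI AE in Phase II (53% on 25 mg, 48% on the corresponding placebo). These include diarrhea, which can hardly be progression of constipation, so they cannot stand in for p.

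**6. How far does the PAC-SYM fill the gap?** It has a 14-day recall and is given on treatment at Weeks 4 and 12, but not at Week 8. Dosing runs from Day 2 to Day 85, which is 85 − 2 + 1 = 84 days. The two windows cover 2 × 14 = 28 days, and 28/84 is one third of treatment (visit windows ignored). The domain score is a mean over items and carries no onset date, duration, causality or action taken. The Week 14 assessment is not required of patients who enter the 52-week study.

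**The case against.** The strongest reply is that keeping worsening of the treated condition out of AE reporting, with SAEs kept in, is a legitimate way to separate tolerability from lack of effect. Where the line falls is then a matter of judgement. That stands in part: the rule is a deliberate exception, and it is not an error.

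Several mitigations are real. The investigator must positively judge that OIC has worsened, and does so blinded. The protocol repeatedly presents abdominal pain to investigators as a drug event. Severe persistent or progressive pain is evaluated urgently, and new clinically relevant findings on physical examination are reported as AEs. The PAC-SYM is patient-completed and summarized by arm. None of this puts a mild or moderate pain back into the AE tables once it has been called OIC.

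A second reply is that the remedy brings its own bias, because lack-of-effect events, perhaps more frequent on placebo, would enter overall AE incidence. This is a fair downside but not a reason to filter beforehand. The protocol already collects AEs irrespective of relatedness, and Appendix B classes deterioration through lack of effect as not related, so the by-causality table would show it.

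A reader might infer more than the text supports, in three ways:
- **An inconsistency with the laboratory rule.** That rule reads "Deterioration of a laboratory value, which is unequivocally due to disease progression, should not be reported as an AE/SAE". Its stricter wording governs a wider exemption that drops SAEs too, so the difference in threshold shows no inconsistency.
- **A flaw in the search for withdrawal effects.** Section 11.2.1 says "Adverse events occurring after the last dose of study drug will also be summarized, which among other purposes, may assess any potential withdrawal-type effects". That is a possible use among others, and limiting the exemption would still leave rebound constipation unrecorded. It does not carry the point.
- **A contradiction with the AE definition or the collection rule.** An explicit exception to a general rule does not contradict it.

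**Conclusion.** The point holds as an inexpensive improvement. The exemption is fixed too broadly for this study: it has no symptom limit and no exception for discontinuation, and it lets an opinion formed before recording remove a leading tolerability symptom from tables that serve the primary objective.

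No magnitude is claimed. Whether the active-placebo difference would be understated, overstated or little changed cannot be told from the protocol. A reader might infer that the rule flatters the drug, but nothing in the document supports a direction. The conclusion assumes only that some investigators would attribute some non-serious abdominal pain or cramping to OIC, which the protocol's own description of the condition permits. SAE reporting is unaffected.

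**What to change.** Reword Underlying disease progression in Section 6.3.4 along these lines: *Non-serious worsening of constipation itself (stool frequency or consistency) need not be recorded as an AE. New or worsened abdominal pain or cramping is recorded as an AE even when OIC is suspected, and so is any event leading to discontinuation of study drug. The investigator then answers the usual causality question.* Little is lost on constipation, which stays visible through PAC-SYM, bisacodyl counts, enema records and OIC healthcare use.

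Costs and downsides:
- No new visits, forms or procedures are needed, only revised wording and a line in site training.
- There would be more non-serious AE entries, possibly more on placebo. The discontinuation clause would also bring in patients who stop because constipation worsened. Entries due to lack of effect would be rated not related under Appendix B.
- The recording rule might differ from that of the pivotal study, which is not shown, within one 24-week exposure. The sponsor should check this and disclose any difference. Section 12.2.1 plans to combine exposure with the pivotal study but does not say that AE tables will be pooled, so the consequence should be small.
- If the change counts as substantial, Section 8.5 requires an amendment approved by each ethics committee, and by the national authority where applicable, across approximately 120 centers.
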